11.4.1.2. Derivations and Handling of Missing Baseline Data

Definition	Reporting Details
Change from Baseline	= Post-Baseline Visit Value – Baseline
[% Change from Baseline]	= [(Post-Baseline Visit Value – Baseline) / Baseline] x 100]

NOTE :

- Unless otherwise specified, the baseline definitions specified in [11.4.1.1Baseline Definitions](#) will be used for derivations for endpoints / parameters and indicated on summaries and listings.
- Unless otherwise stated, if baseline data is missing no derivation will be performed and will be set to missing.
- The baseline definition will be footnoted on all change from baseline displays.

11.4.2. Reporting Process & Standards

Reporting Process	
Software	

 The currently supported versions of SAS and R software will be used to perform all data analyses, generate tables, figures, and listings. 	
Reporting Area	
HARP Server	: Us1salx00259-HARP PROD-US
HARP Area	: \ARPROD\GSK1070806\204882
QC Spreadsheet	: \ARWORK\GSK1070806\204882\ReportingEffort\Documents
Analysis Datasets	

 Analysis datasets will be created according to Integrated Data Standards Library standards. 	
Generation of RTF Files	

 RTF files will be generated for SAC tables. 	

Reporting Standards	
General	

 The current GSK Integrated Data Standards Library (IDSL) will be applied for reporting, unless otherwise stated: 
 4.03 to 4.23: General Principles 5.01 to 5.08: Principles Related to Data Listings 	

 • 6.01 to 6.11: Principles Related to Summary Tables • 7.01 to 7.13: Principles Related to Graphics 	
Formats	

 • In the top left header on each page of output the study part will be indicated after the protocol number (ie, "204824") • All data will be reported according to the actual treatment the subject received unless otherwise stated. • GSK IDSL Statistical Principles (5.03 & 6.06.3) for decimal places (DP's) will be adopted for reporting of data based on the raw data collected. • Numeric data will be reported at the precision collected on the eCRF. • The reported precision from non eCRF sources will follow the IDSL statistical principles but may be adjusted to a clinically interpretable number of DP's. 	
Planned and Actual Time	

 • Reporting for tables, figures and formal statistical analyses : 
 • Planned time relative to dosing will be used in figures, summaries, statistical analyses and calculation of any derived parameters, unless otherwise stated. • The impact of any major deviation from the planned assessment times and/or scheduled visit days on the analyses and interpretation of the results will be assessed as appropriate. • Reporting for Data Listings: 
 • Planned and actual time relative to study drug dosing will be shown in listings (Refer to IDSL Statistical Principle 5.05.1). • Unscheduled or unplanned readings will be presented within the subject's listings. • Visits outside the protocol defined time-windows (i.e. recorded as protocol deviations) will be included in listings but omitted from figures, summaries and statistical analyses. 	
Unscheduled Visits	

 • Unscheduled visits will not be included in summary tables or figures, unless otherwise stated. • All unscheduled visits will be listed. 	
Descriptive Summary Statistics	
Continuous Data	Refer to IDSL Statistical Principle 6.06.1
Categorical Data	N, n, frequency, %
Reporting of Pharmacokinetic Concentration	

Descriptive Summary Statistics	Refer to IDSL Statistical Principle 6.06.1 Handling NQ values per GUI_51487
Reporting of Pharmacokinetic Parameters	
Descriptive Summary Statistics (Log Transformed Data)	N, n, geometric mean, 95% CI of geometric mean, standard deviation (SD) of logged data and between geometric coefficient of variation (CV _{b/w} (%)): $CV_b (\%) = \sqrt{(\exp(SD^2) - 1)} * 100$ 
(NOTE: SD is the SD of log transformed data)

Parameters Not Being Log Transformed	tmax, first point, last point and number of points used in the determination of Lambda_λz.
Parameters Not Being Summarised	tmax, first point, last point and number of points used in the determination of Lambda_λz.
Listings	Include the first point, last point and number of points used in the determination of Lambda_λz.
Graphical Displays	

 Refer to IDSL Statistical Principles 7.01 to 7.13. The same symbol and line type will be used across figures to represent a given treatment group. X-axis variables of time and dose will be plotted as continuous numeric variables. 	

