11.5. Appendix 5: Derived and Transformed Data

11.5.1. General

Multiple Measurements at One Time Point

- Mean of the measurements will be calculated and used in any derivation of summary statistics but if listed, all data will be presented.
- If there are two values within a time window the value closest to the target day for that window will be used. If values are the same distance from the target then the mean will be taken.
- Subjects having both High and Low values for Normal Ranges at any post-baseline visits for safety parameters will be counted in both the High and Low categories of “Any visit post-baseline” row of related summary tables. This will also be applicable to relevant Potential Clinical Importance summary tables.

Study Day

- Calculated as the number of days from dosing date :
 - [1] Assessment Date = Missing → Study Day = Missing
 - [2] Assessment Date < Transplant Date → Study Day = Assessment Date – Transplant Date
 - [3] Assessment Date \geq Transplant Date → Study Day = Assessment Date – Transplant Date

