11.5.3. Safety

+++ ECG Parameters +++	
RR Interval	

 IF RR interval (msec) is not provided directly, then RR can be derived as : 
 If QTcB is machine read & QTcF is not provided, then : $RR = \left[\left(\frac{QT}{QTcB} \right)^2 \right] * 1000$ If QTcF is machine read and QTcB is not provided, then: $RR = \left[\left(\frac{QT}{QTcF} \right)^3 \right] * 1000$ 	

 If ECGs are manually read, the RR value preceding the measurement QT interval should be a collected value THEN do not derive. 	Corrected QT Intervals

 When not entered directly in the eCRF, corrected QT intervals by Bazett's (QTcB) and Fredericia's (QTcF) formulas will be calculated, in msec, depending on the availability of other measurements. IF RR interval (msec) is provided then missing QTcB and/or QTcF will be derived as : $QTcB = \frac{QT}{\sqrt{\frac{RR}{1000}}}$ $QTcF = \frac{QT}{3\sqrt{\frac{RR}{1000}}}$	

+++ Laboratory Parameters +++	

 If a laboratory value which is expected to have a numeric value for summary purposes, has a non-detectable level reported in the database, where the numeric value is missing, but typically a character value starting with '<x' or '>x' (or indicated as less than x or greater than x in the comment field) is present, the number of significant digits in the observed values will be used to determine how much to add or subtract in order to impute the corresponding numeric value. 
 Example 1: 2 Significant Digits = '< x ' becomes x - 0.01 Example 2: 1 Significant Digit = '> x' becomes x + 0.1 Example 3: 0 Significant Digits = '< x' becomes x - 1. If there is more than one value of a particular parameter for a subject for a visit, the scheduled value will be used in summary; all values will be listed. 	

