11.9.6. Safety Tables

Safety Tables					
No.	Population	IDSL / TST ID / Example Shell	Title	Programming Notes	Deliverable
Adverse Events – Overall					
3.01	All Subjects	AE1	Summary of All Adverse Events		IA1, IA2, SAC
3.02	All Subjects	AE3	Summary of Common Adverse Events by Preferred Term	Common AE = Frequency > 1%	IA1, IA2, SAC
3.03	All Subjects	AE1	Summary of Drug-Related Adverse Events by System Organ Class		IA1, IA2, SAC
3.04	All Subjects	AE1	Summary of Serious Adverse Events by System Organ Class		IA1, IA2, SAC
3.05	All Subjects	AE1	Summary of Adverse Events Leading to Withdrawals from Study or Study Treatment		IA1, IA2, SAC
Adverse Events – in patients (before discharge)					
3.06	All Subjects	AE1	Summary of All Adverse Events before Discharge		IA2, SAC
3.07	All Subjects	AE3	Summary of Common Adverse Events by Overall Frequency before Discharge		IA2, SAC
3.08	All Subjects	AE5	Summary of Drug-Related Adverse Events by System Organ Class before Discharge		IA2, SAC

Safety Tables					
No.	Population	IDSL / TST ID / Example Shell	Title	Programming Notes	Deliverable
3.09	All Subjects	AE1	Summary of Serious Adverse Events by System Organ Class before Discharge		IA2, SAC
3.10	All Subjects	AE1	Summary of Adverse Events Leading to Withdrawals from Study / Permanent Discontinuation of Study Treatment before Discharge		IA2, SAC
Adverse Events – out patients (after discharge)					
3.11	All Subjects	AE1	Summary of All Adverse Events after Discharge		IA2, SAC
3.12	All Subjects	AE3	Summary of Common Adverse Events by Overall Frequency after Discharge		IA2, SAC
3.13	All Subjects	AE5	Summary of Drug-Related Adverse Events by System Organ Class after Discharge		IA2, SAC
3.14	All Subjects	AE1	Summary of Serious Adverse Events by System Organ Class after Discharge		IA2, SAC
3.15	All Subjects	AE1	Summary of Adverse Events Leading to Withdrawals from Study / Permanent Discontinuation of Study Treatment after Discharge		IA2, SAC
Labs					
3.16	All Subjects	LB1	Summary of Chemistry Changes from Baseline		IA2, SAC

Safety Tables					
No.	Population	IDSL / TST ID / Example Shell	Title	Programming Notes	Deliverable
3.17	All Subjects	LB1	Summary of Emergent Chemistry Results of Potential Clinical Importance		IA1, IA2, SAC
3.18	All Subjects	LB1	Summary of Haematology Changes from Baseline		IA2, SAC
3.19	All Subjects	LB1	Summary of Emergent Haematology of Potential Clinical Importance		IA1, IA2, SAC
Vital Signs					

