3.20	All Subjects	VS1	Summary of Change from Baseline in Vital Signs	Include the Respiration Rate and Temperature	IA2, SAC
3.21	All Subjects	VS2	Summary of Emergent Vital Signs Results of Potential Clinical Importance		IA1, IA2, SAC
ECGs					
3.22	All Subjects	EG1	Summary of ECG Findings		IA2, SAC
3.23	All Subjects	Non-Standard EFF_T5	Frequency of Maximum Emergent QTc Values by Category		IA1, IA2, SAC
3.24	All Subjects	EG2	Summary of Change from Baseline in ECG Values		IA2, SAC

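### Tables 3.17, 3.19, 3.21 and 3.23 are worst-case safety tables, yet the general rules keep unscheduled and out-of-window readings out of them, so their counts can only err low

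*SAP*

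**What the plan says.** Two rules in SAP Section 11.4.2 decide which readings enter a summary.

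- Unscheduled visits: "Unscheduled visits will not be included in summary tables or figures, unless otherwise stated". They go to listings instead: "All unscheduled visits will be listed".
- Out-of-window visits: "Visits outside the protocol defined time-windows (i.e. recorded as protocol deviations) will be included in listings but omitted from figures, summaries and statistical analyses". This sentence stands under the data-listings bullet but expressly reaches summaries and analyses, and it has no exception clause.

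Section 11.5.3 adds a laboratory rule for a visit with more than one value of a parameter: "the scheduled value will be used in summary; all values will be listed". Section 11.5.1 averages several measurements at one time point and, for two values in a window, takes the one nearer the target day. None of these rules selects the worst value.

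Section 11.9.6 then lists tables whose titles promise a worst-case view. Table 3.17 is "Summary of Emergent Chemistry Results of Potential Clinical Importance", Tables 3.19 and 3.21 are its counterparts for haematology and vital signs, and Table 3.23 is "Frequency of Maximum Emergent QTc Values by Category". The programming-notes cell is empty for all four.

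**The concern.** Restricting by-visit means to scheduled values is ordinary practice, because it keeps triggered measurements from distorting the average at a visit. A table of maxima or of emergent abnormalities has a different purpose: it should report whether a subject ever crossed a threshold after dosing. Unscheduled readings are often taken because something may be wrong, so leaving them out removes readings that may be the most informative for that purpose.

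The SAP expects such readings. The Time and Events table (Appendix 2) has an unscheduled-visit column marked for vital signs, 12-lead ECG, and haematology, chemistry and urinalysis. All four tables are also marked for IA1, the dose-adjustment review, as well as for IA2 and the final delivery.

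**Working it through.** The SAP gives no figure to reproduce. The check is a search for an exception, followed by the direction and size of the effect.

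**1. Is an exception stated?**

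| Place in the SAP | What it contains | Exception? |
|---|---|---|
| 11.9.6, notes to Tables 3.17, 3.19, 3.21, 3.23 | Empty | No |
| Appendix 10, shell EFF_T5 (Table 3.23) | Footnote only on whether QTcB or QTcF is used | No |
| 8.2.1, note 2 to Table 4 | Promises emergent results by PCI criteria; does not mention visit type | No |
| 11.5.1, any-visit post-baseline row | Counts a subject in both High and Low; then "This will also be applicable to relevant Potential Clinical Importance summary tables" | Does not mention unscheduled or out-of-window readings |
| 11.5.3, laboratory rule | Prefers the scheduled value within a visit | No; points the other way |
| 11.6 and 11.7 | Missing-data rules and PCI limits | No |

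The qualifier in the unscheduled-visit rule is therefore never used for these tables. The out-of-window rule has no qualifier to use.

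**2. Direction.** For one subject, let A be all post-dose readings and S the subset that the rules admit. Since S is part of A:

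- max(S) ≤ max(A), so a subject above an upper limit on S is also above it on A;
- min(S) ≥ min(A), so the same holds for a lower limit.

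Summed over subjects, the count from S is never greater than the count from A. Averaging repeat readings cannot reverse this, because a mean never lies beyond the most extreme value averaged.

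**3. How many scheduled readings there are (Appendix 2).**

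- 12-lead ECG after dosing: discharge, 6 months, 12 months. That is at most 3 per subject, and 1 for a subject not yet at 6 months.
- Haematology, chemistry and vital signs: 4-8 h, day 1, day 2, daily to discharge, discharge, day 30, day 90, 6 and 12 months. Coverage is dense in hospital. After discharge it falls to 4 planned visits (day 30, day 90, 6 months, 12 months).

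**4. How table and listing can disagree.** Take a subject whose three scheduled QTc values are all at or below 530 msec and who has one unscheduled value above 530 msec. Shell EFF_T5 has a category for QTc above 530 msec, but under Section 11.4.2 this subject does not enter it. Listing 17 works from the PCI limit of 450 msec in Section 11.7.2 and shows the reading.

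**5. Weight of one subject.** At the maximum of 30 subjects, 1/30 = 3.3%. At an interim of 8 to 10 subjects, as given in Section 3.1.2, it is 1/10 = 10% to 1/8 = 12.5%. These are the weights of a single subject, not estimates of how much the tables would be in error.

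**The case against.** The strongest reply is that nothing is lost. Unscheduled and out-of-window readings are listed, and PCI Listings 13 (haematology), 14 (chemistry), 17 (ECG) and 18 (vital signs) are delivered at IA1 beside the four tables. The study team also reviews safety throughout (Section 2.3). Any QTc high enough for the 530 msec category already qualifies for Listing 17. This stands. A reader might infer that a serious abnormality would be hidden from the dose review; the SAP does not support that, and the defect is confined to the summary tables.

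Second, an unscheduled laboratory or vital-sign abnormality changes a table only if that subject never met the same criterion at a counted visit. With daily inpatient sampling this limits the effect mainly to the period after discharge. This also stands.

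Third, the any-visit row in Section 11.5.1 might be read to cover every visit. It does not say so, and on that reading it conflicts with Section 11.4.2. The company shells LB1 and VS2 are not reproduced either, so what they would contain by default cannot be seen. The uncertainty is a reason to write the rule down.

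Fourth, the laboratory rule in Section 11.5.3 concerns several values within one visit and does not govern a separate unscheduled visit. That is right; it bears on repeat values only.

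**Conclusion.** The point holds for the four summary tables. Followed as written, the SAP builds tables labelled emergent or maximum from a subset of the known readings. The counts can fall short of the true number of subjects with abnormal values and cannot exceed it, and table and listing can contradict each other in the same report. QTc is the clearest case, with at most three counted readings per subject.

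The size is 3.3% per affected subject at 30 subjects. The number affected is unknown: the SAP gives no rate of unscheduled or out-of-window readings, so 3.3% should not be read as an expected bias.

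A reader might also conclude that late follow-up visits should be moved to the nearest planned visit in the by-visit summaries. That does not follow. It is a separate and debatable choice, it depends on visit windows that the SAP leaves to the protocol, and Section 11.4.2 already says that the impact of major timing deviations will be assessed.

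**What to change.** - In the programming notes of Tables 3.17, 3.19, 3.21 and 3.23, state that every post-dose value counts, including unscheduled, repeat and out-of-window readings. Apply the same statement to any any-visit post-baseline row.
- In Section 11.4.2, name these tables as exceptions to both rules. A programming note alone satisfies the unscheduled-visit rule, but the out-of-window rule has no exception clause and must be amended itself.
- In Section 11.5.1, say that the averaging and closest-to-target rules do not apply to worst-case counts. In Section 11.5.3, limit the preference for the scheduled value to by-visit summaries.
- Leave the by-visit summaries (Tables 3.16, 3.18, 3.20 and 3.24) on scheduled values.

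The cost is a few lines of text and some programming, with no new data. Abnormality counts may rise slightly.

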11.5. Appendix 5: Derived and Transformed Data

11.5.1. General

Multiple Measurements at One Time Point

- Mean of the measurements will be calculated and used in any derivation of summary statistics but if listed, all data will be presented.
- If there are two values within a time window the value closest to the target day for that window will be used. If values are the same distance from the target then the mean will be taken.
- Subjects having both High and Low values for Normal Ranges at any post-baseline visits for safety parameters will be counted in both the High and Low categories of “Any visit post-baseline” row of related summary tables. This will also be applicable to relevant Potential Clinical Importance summary tables.

Study Day

- Calculated as the number of days from dosing date :
 - [1] Assessment Date = Missing → Study Day = Missing
 - [2] Assessment Date < Transplant Date → Study Day = Assessment Date – Transplant Date
 - [3] Assessment Date \geq Transplant Date → Study Day = Assessment Date – Transplant Date

11.5.2. Study Population

Demographics

Age

- GSK standard IDSL algorithms will be used for calculating age where birth date will be imputed as follows:
 - [1] Any subject with a missing day will have this imputed as day ‘15’.
 - [2] Any subject with a missing date and month will have this imputed as ‘30th June’.
- Birth date will be presented in listings as ‘YYYY’.

Body Mass Index (BMI)

- Calculated as **Weight (kg) / [Height (m)]²**

11.5.3. Safety

+++ ECG Parameters +++	
RR Interval	

 IF RR interval (msec) is not provided directly, then RR can be derived as : 
 If QTcB is machine read & QTcF is not provided, then : $RR = \left[\left(\frac{QT}{QTcB} \right)^2 \right] * 1000$ If QTcF is machine read and QTcB is not provided, then: $RR = \left[\left(\frac{QT}{QTcF} \right)^3 \right] * 1000$ 	

 If ECGs are manually read, the RR value preceding the measurement QT interval should be a collected value THEN do not derive. 	Corrected QT Intervals

 When not entered directly in the eCRF, corrected QT intervals by Bazett's (QTcB) and Fredericia's (QTcF) formulas will be calculated, in msec, depending on the availability of other measurements. IF RR interval (msec) is provided then missing QTcB and/or QTcF will be derived as : $QTcB = \frac{QT}{\sqrt{\frac{RR}{1000}}}$ $QTcF = \frac{QT}{3\sqrt{\frac{RR}{1000}}}$	

+++ Laboratory Parameters +++	

 If a laboratory value which is expected to have a numeric value for summary purposes, has a non-detectable level reported in the database, where the numeric value is missing, but typically a character value starting with '<x' or '>x' (or indicated as less than x or greater than x in the comment field) is present, the number of significant digits in the observed values will be used to determine how much to add or subtract in order to impute the corresponding numeric value. 
 Example 1: 2 Significant Digits = '< x ' becomes x - 0.01 Example 2: 1 Significant Digit = '> x' becomes x + 0.1 Example 3: 0 Significant Digits = '< x' becomes x - 1. If there is more than one value of a particular parameter for a subject for a visit, the scheduled value will be used in summary; all values will be listed. 	

11.5.4. Pharmacokinetic

GSK1070806 Derived PK Parameters	

 Refer to PK Guidance document GUI00000051487: Non-compartmental Analysis of Pharmacokinetic Data for more information. 	

11.6. Appendix 6: Premature Withdrawals & Handling of Missing Data

11.6.1. Premature Withdrawals

Element	Reporting Detail
General	
 Subject study completion was defined as Safety who either prematurely withdrawn or completed FU visits and assessments. Withdrawn subjects were not replaced in the study. All available data from subjects who were withdrawn from the study will be listed and all available planned data will be included in summary tables and figures, unless otherwise specified.

11.6.2. Handling of Missing Data

Element	Reporting Detail
General	
 Missing data occurs when any requested data is not provided, leading to blank fields on the collection instrument : 
 [1] These data will be indicated by the use of a “blank” in subject listing displays. [2] Answers such as “Not applicable” and “Not evaluable” are not considered to be missing data and should be displayed as such.
Outliers	
 Any subjects excluded from the summaries and/or statistical analyses will be documented along with the reason for exclusion in the clinical study report.
Biomarkers Free IL-18 Drug Bound IL-18 and total IL-18	
 LLQ will be set as LLQ/2 ULQ will be set as ULQ Values used for the computation of the change from baseline and for summaries, plots and analysis, if deemed applicable. Number of data imputed will be highlighted in the summaries whereas listings will report the values as below LLQ or above ULQ. If more than a third of obs are below LLQ or above LLQ then no imputation will be performed for that subject. To enable the data to be plotted (i.e. some groups may remain below BLQ) this rule may not be applied to Free & Drug Bound IL18 parameters.

11.6.2.1. Handling of Missing Dates

Element	Reporting Detail
General	Partial dates will be displayed as captured in subject listing displays.
Adverse Events	
 The eCRF allows for the possibility of partial dates (i.e., only month and year) to be recorded for AE start and end dates; that is, the day of the month may be missing. In such a case, the following conventions will be

Element	Reporting Detail
	
applied for calculating the time to onset and the duration of the event:
 
 • For a missing start day, the 1st of the month will be used unless this is before the start date of investigational product; in this case the study treatment start date will be used (and hence the event is considered On-treatment as per Section 11.3: Treatment States and Phases). • For a missing stop day, the last day of the month will be used, unless this is after the stop date of study treatment; in this case the study treatment stop date will be used. • Completely missing start or end dates will remain missing, with no imputation applied. Consequently, time to onset and duration of such events will be missing. • Start or end dates which are completely missing (i.e. no year specified) will remain missing, with no imputation applied.

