2.3. Study Design

Overview of Study Design and Key Features	

The diagram illustrates the study timeline. It starts with a 'Screening' phase, followed by an 'Inpatient' phase where a 'Single dose' of 'all-18mAb' is administered. This is followed by an 'Outpatient follow-up' phase. A green arrow points to the 'all-18mAb Single dose' point. Below the timeline, a purple bar represents 'Standard transplant immunosuppression' which begins during the inpatient phase and continues through the outpatient follow-up. The timeline is marked with time points: 12h, 0d (Primary endpoint), 7d, 30d, 90d, 6m, and 12m.
	
Overview of Key Study Design Features	
Design Features :	
 Multi-centre, single arm Bayesian sequential design.
Dosing :	
 A single infusion prior to kidney allograft reperfusion.
Treatment Assignment :	
 Single arm study. All patients will be received GSK1070806. No randomization is needed.
Interim Analysis	
 DGF data will be reviewed sequentially. Safety, tolerability and efficacy data will be reviewed by the GSK study team on an ongoing basis throughout the study. An interim analysis will be performed after recruitment of 8 to 10 patients to review for a consideration of dose adjustment based on an integrated review of safety/tolerability, efficacy, and exposure. Once the last patient completes 7-Days post-transplant, an interim analysis will be performed of all available data for the primary endpoint in addition to supportive efficacy and safety data. The results of this interim analysis will be reviewed by the GSK study team and other relevant GSK staff for internal decision making.

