4. Viral serology will include HIV, HBsAg, anti-HBc, anti-HBs antibodies, and hepatitis C antibody (if hepatitis C antibody positive, a hepatitis C RIBA immunoblot or polymerase chain reaction assay should be reflexively performed on the same sample to confirm the results as per NHS standard procedure), and serology for herpes simplex virus, Epstein Barr virus, and varicella zoster virus.
5. Screening viral status may be the most recent value recorded in the patient's medical records.
6. If BK positive then follow up screening should be implemented.
7. Vital signs will include systolic and diastolic blood pressure, pulse rate, and temperature.
8. Pregnancy testing will be performed in women of childbearing potential. Screening test may be urine or serum.
9. Sampling time points may be adjusted as appropriate based on emerging data.
10. PK sampling time points are as follows: predose, 45 min to 1 hr into infusion (coinciding with biopsy), 4-8 hrs, 24 hrs, 168 hrs (or pre-discharge if discharge before day 7), day 30 day 90, 6 and 12 months. Exact PK sampling time is to be recorded.
11. Blood and urine samples for immunogenicity and biomarker analyses must be collected prior to infusion with GSK1070806
12. For any non-completer a serum sample for immunogenicity testing will be taken 12 mths post-operatively.
13. For subjects who withdraw from study, where possible, assessments should continue according to the Time and Events table. The 6 and 12 mth safety follow-up should be performed.
14. **Samples for subjects from Cambridge site only.**
15. GSK1070806 can be infused any time during the pre-operative and/or intra-operative periods, but infusion must be complete prior to reperfusion of the allograft.

16. Sample to be obtained at time of back-table allograft preparation.
17. Documentation of anaesthetics excluded.

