11.3.3. Treatment States for AE Data

Treatment State	Definition
AE = Pre-Treatment	AE Start Date/Time $<$ Study Treatment Start Date/Time
AE Onset Time Since 1 st Dose (Days)	If Treatment Start Date/Time $>$ AE Onset Date/Time : = AE Onset Date - Treatment Start Date If Treatment Start Date \leq AE Onset Date : = AE Onset Date – Treatment Start Date + 1 Missing otherwise
AE Duration (Days)	AE Resolution Date/Time – AE Onset Date/Time (follow SOP)
AE = Drug-related	If relationship is marked 'YES' on [Inform/CRF OR value is missing.

NOTES:

- If the study treatment stop date is missing then the AE will be considered to be On-Treatment

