11.6.2.2. Handling of Partial Dates

Element	Reporting Detail
Concomitant Medications	
 • Partial dates for any concomitant medications recorded in the CRF will be imputed using the following convention: 
 • If the partial date is a start date, a '01' will be used for the day and 'Jan' will be used for the month • If the partial date is a stop date, a '28/29/30/31' will be used for the day (dependent on the month and year) and 'Dec' will be used for the month. • The recorded partial date will be displayed in listings.
Adverse Events	
 • Any partial dates for adverse events will be raised to data management. If the full date cannot be ascertained, the following assumptions will be made: 
 • If the partial date is a start date, a '01' will be used for the day and 'Jan' will be used for the month. • However, if these results in a date prior to Week 1 Day 1 and the event could possibly have occurred during treatment from the partial information, then the Week 1 Day 1 date will be assumed to be the start date. • The AE will then be considered to start on-treatment (worst case). • If the partial date is a stop date, a '28/29/30/31' will be used for the day (dependent on the month and year) and 'Dec' will be used for the month. • The recorded partial date will be displayed in listings.

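### For an AE with known onset after the infusion date and a missing stop day, SAP 11.6.2.1 imputes a stop before onset and so a negative duration; 11.6.2.2 gives a conflicting uncapped rule

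*SAP*

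**What the plan says.** Three parts of the SAP bear on this point.

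- **Imputation, first rule.** Section 11.6.2.1 covers AE dates recorded with month and year only. Its conventions are "applied for calculating the time to onset and the duration of the event". A missing start day becomes the first of the month, or the treatment start date if that is later. A missing stop day becomes month-end, "unless this is after the stop date of study treatment; in this case the study treatment stop date will be used".
- **Imputation, second rule.** Section 11.6.2.2 also addresses partial AE dates. It first sends them to data management. If the full date cannot be found, a partial stop date is given a last-of-month value, which "will be used for the day (dependent on the month and year"), and December is named for the month. There is no cap at treatment stop.
- **Duration and treatment.** Section 11.3.3 defines AE duration as "AE Resolution Date/Time – AE Onset Date/Time (follow SOP"), with no floor at zero. Section 2.3 describes the treatment as "A single infusion prior to kidney allograft reperfusion", and footnote 15 of Appendix 2 adds that "infusion must be complete prior to reperfusion of the allograft".

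**The concern.** A cap at treatment stop can make sense where dosing continues through follow-up. Here dosing ends on the operating table, or before, while the Appendix 2 schedule runs to 12 months. AEs starting after the infusion date are therefore expected: Appendix 9 plans five tables of them after discharge (3.11 to 3.15, beginning with "Summary of All Adverse Events after Discharge"). For such an AE the cap pulls the stop date back to a day before the event began. The rule then fails at the purpose 11.6.2.1 gives for it, which is to calculate duration.

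The second rule adds a conflict. A programmer following 11.6.2.1 and one following 11.6.2.2 would derive different stop dates from the same record, and the SAP gives no basis for choosing between them.

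**Working it through.** The SAP states no figure on this point, so there is nothing to reproduce. The check applies the rules as written.

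**Inputs**
- Treatment stop date T: the infusion date, from one infusion completed before reperfusion (2.3; Appendix 2, footnote 15).
- Stop rule: imputed stop = min(month-end, T) (11.6.2.1).
- Start rule when the start day is missing: max(first of month, treatment start date) (11.6.2.1).
- Duration = stop − onset (11.3.3).
- Assumption for illustration: the infusion starts and stops on 10 January 2017. The other dates are also invented.

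**General result, onset day known.** Let onset be T + k with k ≥ 1. The AE resolves on or after onset, so the end of its resolution month is later than T and the cap always applies. Imputed stop = T, and duration = T − (T + k) = −k. The true duration does not enter. Onset on T itself gives 0.

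**Examples**

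| Recorded onset | Recorded stop | 11.6.2.1 as written | Month-end without cap |
|---|---|---|---|
| 12 Jan | Jan | 10 Jan − 12 Jan = −2 | 31 Jan − 12 Jan = +19 |
| 15 Mar | Apr | 10 Jan − 15 Mar = −64 | 30 Apr − 15 Mar = +46 |
| Mar (day missing) | Apr | 10 Jan − 1 Mar = −50 | 30 Apr − 1 Mar = +60 |
| Jan (day missing) | Jan | 10 Jan − 10 Jan = 0 | 31 Jan − 10 Jan = +21 |
| Jan (day missing) | Apr | 10 Jan − 10 Jan = 0 | 30 Apr − 10 Jan = +110 |

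The last three rows show the case with both days missing: duration is 0 when the onset month is the infusion month and negative when it is later.

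**Midnight case.** If the infusion runs past midnight, an AE starting on the second calendar date has duration 0. That onset is not after the treatment stop date, so the general result stands.

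**The second rule on the same record.** Take onset 15 March, stop April. Section 11.6.2.2 can be read in two ways:
- The recorded month is kept and December fills only a missing month: 30 Apr − 15 Mar = +46.
- December is used even though the month is known: 31 Dec − 15 Mar = day 365 − day 74 = +291.

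One record therefore gives −64, +46 or +291 days, depending on the section used and how it is read.

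**The case against.** Four points can be made for the plan.

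1. **Other safeguards come first.** Partial AE dates go to data management, and 11.3.3 refers duration to an SOP that is not shown. The query reduces the number of cases, but both imputation rules exist for dates that stay unresolved. The SOP may deal with inconsistent dates, yet nothing in the SAP says that it overrides 11.6.2.1.
2. **The two rules may not overlap.** Because the day in 11.6.2.2 depends on the month, that section may be meant to keep a recorded month, with December reserved for a missing one. It could even be meant only for dates with no month at all. The first reading is sensible, but it leaves the conflict over the cap. The second would remove the overlap, but the section does not limit itself in that way, and 11.6.2.1 itself uses the term partial dates for month-and-year records.
3. **No reported result is shown to change.** This stands. No display title in Appendix 9 names AE duration, and both sections say that listings show the date as recorded. The standard AE listing shells are not reproduced, so it cannot be determined whether derived duration appears in any output.
4. **Frequency is unknown.** This also stands. The study has at most 30 subjects, and the number of unresolved partial stop dates cannot be estimated from the SAP.

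A reader might infer that the safety tables or the DGF result are at risk. The SAP does not support that. Section 11.3.3 classifies AEs by their start, AE counts do not use the stop date, and the primary endpoint does not use AE dates.

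**Conclusion.** The rule is wrong as written, and the impact is minor. For every AE with a known onset after the infusion stop date and a missing stop day, 11.6.2.1 gives a stop before onset and a duration of −k days. This follows from the wording alone; the calendar dates above serve only as illustration. Section 11.6.2.2 conflicts with it by having no cap, and no precedence is stated. The Jan/Dec wording there is a separate ambiguity.

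The effect is confined to the derived stop date and duration of AEs whose partial stop date remains unresolved after the query. The conclusion assumes that the SOP named in 11.3.3 does not replace the imputation rule, which the SAP nowhere says it does.

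**What to change.** - In 11.6.2.1, delete the cap at treatment stop. Impute a missing stop day as the earlier of month-end and the date of last contact or death, and never before the AE onset date. If last contact falls after April, the March-to-April example then gives +46 days.
- Do not put the cap at withdrawal or study completion instead. Footnote 13 of Appendix 2 keeps assessments going after withdrawal where possible, with the 6- and 12-month safety visits still due, and 11.6.1 counts withdrawn subjects as completing. Either cap could again fall before onset.
- Merge the AE parts of 11.6.2.1 and 11.6.2.2 into one partial-date rule. Keep the data-management query as the first step, and use January or December only when the month itself is missing.

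The cost is SAP wording and the matching derivation code. No new data are needed. With the cap gone and the recorded month kept, a known onset can no longer give a negative duration, and month-end overstates the true duration by at most 30 days (31 − 1).
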